## **Statistical Analysis Plan**

 Treatment Emergent Serious AEs (TESAEs) leading to discontinuation of study by SOC and PT

If more than one event occurred with the same preferred term for the same subject, the subject will be counted only once for that preferred term using the most severe or related occurrence for the summary by severity, or relationship to study drug, respectively.

The following listing will be created:

- All TEAEs
- All TESAEs
- All TEAEs Leading to Study Discontinuation
- All TEAEs leading to Deaths

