## 7. SUMMARY OF STUDY DATA

## 7.1. Subject Disposition

A summary of the analysis sets includes the number and percentage for the following categories

- the number of subjects dosed in the original parent study (PTI-125-04 Safety Population)
- the number enrolled in the OLE (OLE Safety Population)
- the number of subjects who completed 96 weeks in the OLE (OLE Safety Population)
  - subject who completed 96 weeks in the OLE and reconsented and resumed study participation (OLE Safety Population) will be identified via footnote
- the number of subjects who discontinued treatment early in the OLE and reason(s) for discontinuation of treatment as recorded on the OLE eCRF

A by-subject data listing of study completion information including the reason for premature study withdrawal, if applicable, will be presented.

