### 8.1. Adverse Events

The Medical Dictionary for Regulatory Activities (MedDRA) dictionary (v27.0) will be used for coding AEs on the OLE Adverse Event eCRF.

Analyses of AEs will be performed for those events that are considered treatment emergent (TEAE), where treatment emergent is defined as any AE with onset or worsening on or after the First Study Dose in the OLE study and will be summarized for overall safety population.

The following summary tables will be presented:

- Overall Summary of TEAEs
- TEAEs by system organ class (SOC) and preferred term (PT)
- TEAEs by PT
- TEAEs by SOC, PT, and Maximum Severity
- TEAEs by SOC, PT, and Relationship to Study Drug
- Treatment Emergent Serious AEs (TESAEs) by SOC and PT

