## 9. TABLES AND LISTINGS

## Table 1: Data Summary Tables and Listings

Table Number	Table Title	Population		
14.1	Demographic Data			
14.1.1	Disposition			
	Summary of Subject Dispositions	Safety Analysis Population		
14.1.2	Demographics			
	Summary of Demographics and Baseline Characteristics	Safety Analysis Population		
14.3	Safety Data			
14.3.1	Displays of Adverse Events			
14.3.1.1	Summary of Treatment Emergent Adverse Event	Safety Analysis Population		
14.3.1.2	Summary of Treatment Emergent Adverse Event by System Organ Class and Preferred Term	Safety Analysis Population		
14.3.1.3	Summary of Treatment Emergent Adverse Event by Preferred Term	Safety Analysis Population		
14.3.1.4	Summary of Treatment Emergent Adverse Event by System Organ Class, Preferred Term and Maximum Severity	Safety Analysis Population		
14.3.1.5	Summary of Treatment Emergent Adverse Event by System Organ Class, Preferred Term and Relationship to Study Drug	Safety Analysis Population		
14.3.1.6	Summary of Treatment Emergent Serious Adverse Event by System Organ Class, Preferred Term	Safety Analysis Population		

14.3.1.7	Summary of Treatment Emergent Serious Adverse Event led to discontinuation of study by System Organ Class, Preferred Term	Safety Analysis Population	
Listing Number	Listing Title	Population	
16.2	Participant Data Listings		
16.2.1	Discontinued Subjects		
	Participant Disposition	Safety Analysis Population	
16.2.4	Demographic Data		
	Demographic and Baseline Characteristics	Safety Analysis Population	
16.2.7	Adverse Event Listing		
16.2.7.1	Listing of All TEAEs	Safety Analysis Population	
16.2.7.2	Listing of All TESAEs	Safety Analysis Population	
16.2.7.3	Listing of All TEAEs Leading to Study Discontinuation	Safety Analysis Population	
16.2.7.4	Listing of All TEAEs Leading to Deaths	Safety Analysis Population

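### The only planned table of adverse events leading to discontinuation is limited to serious events, while the matching listing covers all of them

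*SAP*

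**What the plan says.** SAP 8.1 lists seven AE summary tables. The last is "Treatment Emergent Serious AEs (TESAEs) leading to discontinuation of study by SOC and PT". In the SAP 9 index this is Table 14.3.1.7, "Summary of Treatment Emergent Serious Adverse Event led to discontinuation of study by System Organ Class, Preferred Term". The restriction to serious events appears in both places, so it is not a slip in one of them.

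Among the AE listings, both sections extend the discontinuation listing to every TEAE. Its index entry, 16.2.7.3, reads "Listing of All TEAEs Leading to Study Discontinuation".

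Other planned outputs touch the same subjects:

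- The general TEAE tables include non-serious events. They are the SOC/PT table (14.3.1.2, "Summary of Treatment Emergent Adverse Event by System Organ Class and Preferred Term"), the PT table (14.3.1.3), the severity table (14.3.1.4, "TEAEs by SOC, PT, and Maximum Severity") and the relationship table (14.3.1.5, "TEAEs by SOC, PT, and Relationship to Study Drug").
- Table 14.3.1.1 is described in SAP 8.1 only as "Overall Summary of TEAEs". Its rows are not specified.
- The disposition table (SAP 7.1, Table 14.1.1) reports "the number of subjects who discontinued treatment early in the OLE and reason(s) for discontinuation of treatment as recorded on the OLE eCRF". SAP 7.1 also plans a by-subject listing of study completion with the reason for withdrawal.

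**The concern.** SAP 3.1 states the objective as long-term safety and tolerability. Adverse events that make a subject leave a study bear directly on tolerability, and they need not be serious: seriousness under Protocol 9.4 depends on outcomes such as death, hospital admission or lasting disability. A table filtered on seriousness shows only part of the picture, and a reader who takes it as the summary of AE discontinuations may not notice what is missing.

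The AE outputs also carry more weight here than usual. SAP 3.1 drops the descriptive summaries of vital signs, laboratory tests and ECGs. SAP 8.2 to 8.5 drop the individual listings and rely on investigators reporting significant findings as AEs. The AE tables are therefore where most of the summarized safety information will be found.

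**Working it through.** No sample size, power or error rate is involved. The check is a count of the planned outputs, matching SAP 8.1 to the index in SAP 9.

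| Output | Events covered | Breakdown | Identifies discontinuation? |
|---|---|---|---|
| 14.3.1.1 | TEAEs | rows not specified | not stated |
| 14.3.1.2 | all TEAEs | SOC, PT | no |
| 14.3.1.3 | all TEAEs | PT | no |
| 14.3.1.4 | all TEAEs | SOC, PT, severity | no |
| 14.3.1.5 | all TEAEs | SOC, PT, relationship | no |
| 14.3.1.6 | serious only | SOC, PT | no |
| 14.3.1.7 | serious only | SOC, PT | yes |
| Listing 16.2.7.1 | all TEAEs | by subject | no |
| Listing 16.2.7.2 | serious only | by subject | no |
| Listing 16.2.7.3 | all TEAEs leading to study discontinuation | by subject | yes |
| Listing 16.2.7.4 | TEAEs leading to death | by subject | no |

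**Tables.** There are 7 AE tables, of which 6 are by SOC/PT or by PT (14.3.1.2 to 14.3.1.7); 5 of the 6 are strictly by SOC and PT, since 14.3.1.3 is by PT alone. Of the 6, 4 cover all TEAEs and 2 are serious only (4 + 2 = 6). One of the 6 identifies discontinuation, and it is serious only. The number that identify a non-serious TEAE as leading to discontinuation is 0, whether the base is 6 or 5.

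**Listings.** Of 4 AE listings, 2 include non-serious events that led to study discontinuation (16.2.7.1 and 16.2.7.3), and 1 identifies them as such (16.2.7.3).

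**Size of the undercount.** Let D be the number of subjects who left the study because of any TEAE, and S the number of those with at least one serious TEAE leading to discontinuation. Table 14.3.1.7 can show at most S subjects, so it omits D − S, a fraction (D − S)/D of the AE discontinuations. The documents give neither D nor S, only an enrolment cap of 180 (SAP 5). The omission can be anything from none (every case serious) to all D (no case serious), and nothing in the plan narrows that range.

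**Whether the records exist.** Protocol 9.1 requires withdrawal from the study because of an AE to be recorded on the eCRF, without regard to seriousness. Listing 16.2.7.3 already depends on the same records.

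**The case against.** The strongest reply is that nothing is contradicted or breached. The text and the index of the SAP agree with each other, and a table of a subset can stand beside a listing of the full set. Protocol 10.2 specifies no discontinuation table. SAP 2.1 says openly that this is an abbreviated plan for a closing program with no full study report expected, and SAP 2.2 says only that the results may be used in the safety update report. The events are not lost. The study is single-arm with no inferential statistics (SAP 6.4.1), and the number of subjects affected could be zero.

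Most of this stands as a limit on weight. It does not explain why two outputs under the same discontinuation heading use different filters, and the SAP gives no reason. The substitutes are also incomplete. The listing has no counts or percentages by SOC and PT. The disposition table concerns treatment rather than study and has no SOC/PT breakdown. The overall summary may or may not carry a total. Because analyses run from ADaM datasets (SAP 6.3.6), the missing count could be programmed and need not be tallied by hand, but as the plan stands that would be an unplanned output.

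A second fair point concerns stopping drug as opposed to leaving the study. The liver and C-SSRS criteria in Protocol 7.1 can be met without a serious event, but they concern study drug, and Protocol 8 separates stopping drug from stopping participation. A table filtered on study discontinuation would still miss a subject who stopped drug for a non-serious event but was not recorded as leaving the study because of it. The main fix does not close that gap.

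**Conclusion.** The concern holds. Followed exactly, the plan yields a discontinuation table that shows only the serious part of the AE discontinuations, and no SOC/PT table supplies the rest. This should be corrected because it bears on the tolerability objective and the correction is cheap. Its weight is modest: no data are lost and no inferential result changes.

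The conclusion rests on the output titles being programmed as written. It assumes nothing about how many non-serious discontinuations occurred. The documents do not show whether the restriction was deliberate; if it was, the SAP should say why.

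**What to change.** In SAP 8.1 and SAP 9, retitle and refilter Table 14.3.1.7 so that it counts all TEAEs leading to discontinuation of the study, by SOC and PT, with an 'of which serious' column. It then matches Listing 16.2.7.3 and keeps every number now planned. Add a footnote that Table 14.1.1 counts discontinuation of treatment, so its totals may differ.

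Optionally, extend the table to events leading to discontinuation of study drug, but only if the sponsor confirms that the eCRF links drug discontinuation to a specific AE.

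The cost is one title, one filter, one column and one footnote. The plan stays at 7 AE tables and 4 AE listings and needs no data beyond those Listing 16.2.7.3 already requires. SAP 2.2 calls for sponsor and vendor approval before database lock and for a Note to File on material deviations, so the change also needs a minor SAP revision or such a note.

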### 7.1. STOPPING CRITERIA

Liver chemistry threshold stopping criteria have been designed to ensure subject safety and to evaluate liver event etiology during administration of study drug. Potential discontinuation of study drug for abnormal liver function tests should be considered by the Investigator in consultation with the designated medical monitor if the study subject meets one or more of the following criteria:

- ALT or AST  $\geq 4x$  ULN;
- ALT or AST  $\geq 3x$  ULN and total bilirubin  $\geq 2x$  ULN;
- ALT or AST ≥ 3x ULN if associated with the appearance or worsening of fatigue, nausea, vomiting, right upper quadrant pain or tenderness, fever, rash and/or eosinophilia; or
- ALP elevations, if deemed of liver origin and drug-related as follows:
  - o ALP > 3x ULN;
  - o ALP > 2.5x ULN and total bilirubin > 2x ULN; or
  - o ALP > 2.5x ULN if associated with the appearance or worsening of fatigue, nausea, vomiting, right upper quadrant pain or tenderness, fever, rash and/or eosinophilia.

In the event of discontinuation due to abnormal liver function tests, the subject will be appropriately investigated to determine the potential cause and referred to a physician experienced in the treatment of hepatic disorders.

Study drug should be discontinued if a subject: (1) positively affirms suicidal ideation in response to questions number 4 or 5 in the suicidal ideation section of the C-SSRS, or (2) reports any suicidal behavior or non-suicidal self-injurious behavior since their last visit in response to the C-SSRS Suicidal Behavior questions. The subject should be referred to a psychiatrist or an appropriate health care professional for further evaluation and management.

An additional stopping criterion will be bodyweight loss of  $\geq$  2 kg resulting in a BMI < 18.5.

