### 8. EARLY DISCONTINUATION

Subjects, Investigators, and the Sponsor may choose to have a subject discontinue study drug or study participation at any time, for any reason, and without prejudice.

The following must be completed and documented in the source documents and the electronic case report forms (eCRFs) for all subjects who discontinue the study early:

- The reason for early study discontinuation.
- Vital signs (blood pressure, temperature, pulse, and respiratory rate), height, weight, full physical exam, clinical laboratory tests, ECG, use of concomitant medications, and adverse events should be obtained at discharge prior to release.
- Administer the C-SSRS Since Last Visit version. If the C-SSRS indicates imminent
  risk for suicidality, defined as the subject positively endorsing questions 4 or 5 of the
  suicidal ideation section or any suicidal behavior questions, immediately contact the
  sponsor.

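### The AE-discontinuation outputs are triggered by leaving the study, while the liver and C-SSRS stopping criteria and the disposition summary concern stopping the drug

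*SAP*

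**What the plan says.** SAP 8.1 plans one summary table on discontinuation, "Treatment Emergent Serious AEs (TESAEs) leading to discontinuation of study by SOC and PT", and one listing, "All TEAEs Leading to Study Discontinuation". The index in SAP 9 repeats both: Table 14.3.1.7 is titled "Summary of Treatment Emergent Serious Adverse Event led to discontinuation of study by System Organ Class, Preferred Term" and Listing 16.2.7.3 is "Listing of All TEAEs Leading to Study Discontinuation". No table or listing is named for events that led to stopping study drug.

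The protocol's main rules are written about the drug. The liver criteria in Protocol 7.1 begin: "Potential discontinuation of study drug for abnormal liver function tests should be considered by the Investigator". The C-SSRS criterion in the same section also acts on study drug, and so does the C-SSRS instruction at each visit except End of Study / Early Termination. The weight-loss criterion does not name what is stopped. Protocol 8 says that subjects, investigators and the sponsor "may choose to have a subject discontinue study drug or study participation at any time", so it offers two choices.

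SAP 7.1 uses both terms. Its summary reports "the number of subjects who discontinued treatment early in the OLE and reason(s) for discontinuation of treatment as recorded on the OLE eCRF". Its by-subject listing gives the reason for withdrawal from the study.

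**The concern.** The only objective is long-term safety, and a reader of the safety output will want to know which events caused simufilam to be stopped. The planned outputs answer a different question: which events caused a subject to leave the study. Where the two differ, the disposition summary can show a treatment discontinuation for an adverse event while neither AE-discontinuation output names that event.

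The rest of the output offers little to fall back on. SAP 3.1 drops the descriptive summaries of vital signs, laboratory parameters and ECGs. SAP 8.2 to 8.5 drop the listings of laboratory, vital sign, physical examination and ECG results. SAP 9 includes no C-SSRS output, although SAP 6.4.1 says in general terms that all data will be listed by subject. An event that met a stopping criterion therefore reaches the reader mainly through the AE outputs. Protocol 2.2 describes liver findings in rats and says that their species specificity is still being evaluated, so whether a liver event stopped the drug is a natural question here. SAP 2.1 does not expect a full clinical study report, so no later document may fill the gap.

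**Working it through.** No arithmetic applies. Neither document gives a discontinuation rate, an event count or the size of the Safety population, so the check is a comparison of definitions.

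**Step 1: what triggers each item.**

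| Place | What is discontinued |
|---|---|
| Protocol 7.1, liver criteria | study drug |
| Protocol 7.1, C-SSRS criterion | study drug |
| Protocol 8, opening sentence | study drug or participation, as alternatives |
| Protocol 8, required records | reason for leaving the study |
| Protocol 9.1, eCRF rule for AE withdrawals | the study |
| SAP 7.1, disposition summary | treatment |
| SAP 7.1, by-subject listing | the study |
| SAP 8.1 and 9, Table 14.3.1.7 | the study, serious events only |
| SAP 8.1 and 9, Listing 16.2.7.3 | the study, all TEAEs |

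No sentence in either document says that stopping drug and leaving the study are the same event.

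**Step 2: follow a subject through the outputs.**

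- *Case A.* An event stops the drug and the subject is recorded as leaving the study because of that event. Listing 16.2.7.3 includes the event, Table 14.3.1.7 counts it if serious, and both parts of SAP 7.1 agree.
- *Case B.* An event stops the drug, but the recorded reason for leaving the study is something else, such as withdrawn consent or closure by the sponsor. The disposition summary counts a treatment discontinuation for the event, and the disposition listing shows the other reason. Listing 16.2.7.3 omits the event. Table 14.3.1.7 omits it even if it is serious.

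In Case B the event still appears in Listing 16.2.7.1 and in the SOC, preferred-term, severity and relationship tables. Only its identification as leading to discontinuation is lost. The overall TEAE summary (Table 14.3.1.1) might carry a discontinuation row, but the SAP does not describe its contents.

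**Step 3: can Case B occur?** Protocol 8 allows it. After a liver discontinuation, Protocol 7.1 calls for investigation of the cause and specialist referral, and does not say that the subject leaves the study. On the other side, Appendices B and C dispense drug at every scheduled visit except Re-entry Week 4, where Protocol 7.2.9 returns the existing bottle, and End of Study / Early Termination. No off-drug visit is scheduled. Case B is possible under the text but may be uncommon.

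**The case against.** The strongest reply is that the two events coincide in practice. There is no off-drug visit schedule. Protocol 9.1 follows subjects withdrawn for an adverse event until it resolves or stabilises, so safety follow-up does not require staying in the study. The procedures in Protocol 8 are written only for those who leave the study early. SAP 7.1 uses treatment and study wording side by side, which suggests loose terminology in an abbreviated SAP more than two deliberate definitions. If the OLE eCRF has a single discontinuation form, the two reasons may be one field.

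Much of this stands. It limits how often the gap can arise, and it rules out reading the SAP as having chosen to leave out drug stops. It does not close the gap, because neither document equates the two events and Protocol 8 separates them.

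Three stronger readings are tempting and are not supported:

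- A reader might infer that the event disappears from the report. It does not: every TEAE is listed and tabulated.
- A reader might convert missed subjects into percentage points of the 180 in SAP 5. That figure is an enrolment cap, any count of subjects would be a guess, and no all-TEAE discontinuation percentage is planned. Listing 16.2.7.3 carries no percentages, and Table 14.3.1.7 is confined to serious events.
- A reader might infer that, because the program closed, sponsor termination was probably the exit reason recorded for subjects already off drug. The documents do not show how exits were recorded.

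**Conclusion.** The mismatch is real and can be read directly from the text. As written, both AE-discontinuation outputs can omit an event that stopped simufilam when the subject is not recorded as leaving the study because of it. They also need not agree with the disposition summary. The consequence is loss of a label on an event that is still reported elsewhere. Its size cannot be derived and may be small.

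The conclusion rests on two assumptions: that stopping drug and leaving the study can be recorded separately or with different reasons, which Protocol 8 permits but the eCRF would have to confirm; and that the outputs are programmed to the titles in SAP 8.1 and 9. The restriction of Table 14.3.1.7 to serious events is a separate issue. A non-serious event would be absent from that table under either trigger.

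**What to change.** In SAP 8.1 and SAP 9, change the trigger of Listing 16.2.7.3 and Table 14.3.1.7 to discontinuation of study drug or of the study, and show which of the two occurred. Take the treatment-discontinuation reason that SAP 7.1 already draws from the OLE eCRF, and link it to the AE record where the eCRF allows. A subject-level reason does not by itself identify the causal event. The documents do not describe a linking field, so where there is none the SAP should say how the event is identified. Use the same term in the SAP 7.1 summary and listing, and reconcile the AE-discontinuation outputs with disposition, allowing for the serious-only scope of the table.

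If the sponsor can confirm that every drug stop for an adverse event was also recorded as leaving the study for that event, one sentence in the SAP saying so would settle the point.

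No stopping criterion, visit or planned data collection changes. The cost is SAP wording, slightly more programming, some data review if no link exists, and possibly a few more events listed. SAP 2.1 places approval before database lock, which leaves room for the change. If the SAP is already approved, the Note to File in SAP 2.2 can record it.

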## 8.2. Clinical Laboratory Evaluations

Listings of individual laboratory parameters by visit will not be presented. Significant laboratory results, as assessed by the Investigators, will be tabulated as AEs or SAEs and will appear in individual AE listings.

## 8.3. Vital Signs

Listings of vital sign results will not be presented. Significant vital sign values, as assessed by the Investigators, will be tabulated as AEs or SAEs and will appear in individual AE listings.

## 8.4. Physical Examination

Listings of individual physical examinations results will not be presented. Significant results, as assessed by the Investigators, will be tabulated as AEs or SAEs and will appear in individual AE listings.

## 8.5. Electrocardiograms (ECG)

Listings of individual ECG parameters (including HR, PR, QRS, QT and QTCF) will not be presented. Significant results, as assessed by the Investigators, will be tabulated as AEs or SAEs and will appear in individual AE listings.

